### ***Hypothesis 1: Is EEG Guidance Intervention Associated with Reduced One-Year Mortality?***

*Patient Population:* Patients randomized to intervention or control (N = 1232)

*Primary Predictor Variable:* EEG guidance intervention

(X=0 for control or X=1 for intervention)

Intention to treat

*Outcome:* Mortality, with one-year follow up

- Any patient who is lost to follow up before one year will be right-censored at the time of last follow-up. (No assumptions are made about vital status after the date of last follow up.)

*Data Description Plan:* Kaplan-Meier curves, stratified by intervention group

*Analysis Plan:* Cox proportional hazards regression for one-year mortality

- Will perform unadjusted and adjusted analyses
- Will adjust for age, sex, American Society of Anesthesiologists (ASA) physical status classification (1-2 vs 3 vs 4-5), number of comorbid conditions, baseline poor functional capacity (<4 METS), history of falls (yes/no within previous 6 months), evidence of abnormal cognition (preoperative Short Blessed Test score > 4), surgery type (cardiac versus non-cardiac), length of anesthesia (Anesthesia Stop – Anesthesia Start)
  - o Multiple imputation may be used to address missing values of these variables

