METHODS AND ANALYSIS: This is a 1,232 patient, block-randomized, double-blinded, comparative effectiveness trial. Patients older than sixty, undergoing volatile agent-based general anesthesia for major surgery, are eligible. Subjects are randomized to one of two anesthetic approaches. One group receives general anesthesia with clinicians blinded to EEG monitoring. The other group receives EEG-guidance of anesthetic agent administration. The outcomes of postoperative delirium (≤ 5 days), falls (≤ 1 month) and health-

between groups will be presented with 95% confidence intervals, and will be considered statistically significant at a two-sided $p<0.05$.

ETHICS AND DISSEMINATION: ENGAGES is approved by the ethics board at Washington University.

Recruitment began in January 2015. Dissemination plans include presentations at scientific conferences, scientific publications, internet-based educational materials, and mass media.

REGISTRATION DETAILS: ENGAGES is registered on clinicaltrials.gov, NCT02241655 (updated February 2015).

Strengths

- The ENGAGES study is a pragmatic clinical trial, conducted in a real world clinical setting.
- The study will enroll older patients, who are under-studied in clinical research.
- The primary outcome, postoperative delirium, is important to patients, healthcare providers and society.
- The electroencephalography-guided anesthetic protocol is straightforward and inexpensive; it would be feasible to disseminate and implement broadly.
- The study utilizes reliable and granular data from the perioperative electronic medical record and incorporates data from a large registry of postoperative patient reported outcomes.

Limitations

- A single clinical trial should seldom be regarded as definitive; if the results of this trial do suggest that EEG-guidance of anesthesia decreases postoperative delirium, it will be necessary to replicate this finding in future studies.
- While patients and those assessing the primary outcome are blinded, the inability to blind clinicians to the trial allocation group is a potential source of bias and confounding.
- The effectiveness of the electroencephalography-guided anesthetic protocol will depend on clinicians' adherence to the protocol.
- As delirium is a fluctuating disorder, it may occasionally be missed despite rigorous and validated assessment methods.

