- Some patients might be unable to speak in the early postoperative period (e.g. have a tracheal tube in place), which will curtail the sensitivity of delirium assessment.

Background

Within the next forty years, >110 million Americans will exceed the age of 60,¹ and many of them (>40%) will require elective surgery.² The geriatric syndrome of postoperative delirium is one of the most common complications observed with the physiological stress of major surgery and anesthesia. It affects up to 70% of surgical patients older than 60, with most studies showing an incidence of 30% to 50%.³ Delirium is an acute and fluctuating neurologic disorder that reflects a change from baseline cognition and is characterized by the cardinal features of inattention and disorganized thinking.⁴ Postoperative delirium typically first manifests between 24 and 96 hours following the surgical intervention. While it is unclear why postoperative delirium occurs so frequently, consistently described risk factors for delirium include older age, male sex, mild cognitive impairment, dementia, sensory impairment, and chronic medical illness.⁵

Postoperative delirium has substantial implications at a societal level, for healthcare professionals and for individual patients and their families. It is estimated that delirium is associated with additional healthcare costs exceeding \$60,000 per patient per year.⁶ Both the occurrence and the duration of delirium are linked with increased morbidity and mortality, prolonged length of hospital and intensive care unit (ICU) stay, as well as functional and cognitive decline necessitating nursing home or long-term care facility placement.⁷⁻¹⁰ Preoperative surveys completed by 1,000 patients at our institution, Barnes-Jewish Hospital, a tertiary care facility at Washington University in St. Louis, showed that approximately 40% of surgical patients highlight postoperative delirium (or acute confusion) as one of their top concerns, and 30% of all patients are worried that they will still have problems thinking normally when they return home to recover. Another survey study showed that, when in-hospital delirium occurs, patients' family members are deeply affected by both the acute neurologic deterioration and the impact upon recovery.¹¹

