Cognitive Testing

When patients are assessed for delirium, structured cognitive appraisal is performed, which gives the interviewer an opportunity to make observations that are used when scoring the CAM. In addition, as part of the routine preoperative assessment, patients will be screened for cognitive impairment with the AD-8 dementia screen⁸⁰ and with the Short Blessed Test.⁸¹ Tests from the cognitive battery of the NIH toolbox might also be incorporated in the baseline assessment.^{82,83} This computer based battery assesses Executive Function, Attention, Episodic Memory, Language, Processing Speed and Working Memory (See Appendix). Depending on time constraints, patients might complete a long form of the cognitive battery or a version focused on executive function, episodic memory and attention. Patients who prefer not to do computer based cognitive tests will be offered paper based cognitive tests (Trails A and B, and Stroop Color and Word Test). Impaired performance on preoperative cognitive tests is reportedly associated with postoperative delirium^{84,85}, and postoperative delirium has been found to be associated with persistent postoperative cognitive decline.¹⁸ Therefore, when patients are followed up postoperatively at thirty days, the Short Blessed Test will be administered on the telephone. When patients are followed up postoperatively at one year, the Short Blessed

(hematocrit <35%), functional status, 6 months history of falls and the Barthel Index.⁸⁶ In addition to these measures, for the ENGAGES study we plan to measure grip strength and the Timed Up and Go (TUG) test.⁸⁶ Grip strength will also be assessed with three measurements in the dominant hand using a Jamar® handheld dynamometer (Lafayette Instruments, Lafayette, IN).⁸⁷ Maximal grip strength will be selected for analysis.

Patients' Postoperative Health and Wellbeing

All patients enrolled in the ENGAGES study will already have provided informed consent for the SATISFY-SOS study. Using the SATISFY-SOS infrastructure, the ENGAGES study will track postoperative patient reported outcomes at approximately 1 month and at 1 year. Patient reported outcomes tracked include health-related quality of life and postoperative falls.

Outcome Measures

i) Incidence of Postoperative Delirium (Aim 1 in Figure 2)

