We will follow the intention-to-treat principle for all analyses. The primary endpoint of our analysis is the incidence of postoperative delirium as defined previously. The incidence of delirium will be compared between groups using a chi-square test, and the difference in delirium incidence with 95% confidence intervals will be calculated. Prespecified exploratory subgroup analyses: we will test for effect modification by known baseline delirium risk factors (i.e., age [<70 and ≥ 70], sex, history of falls, and type of surgery [cardiac versus non-cardiac]).

ii) Effectiveness of EEG-guided anesthesia protocol in improving patient reported outcomes of health-related quality of life and preventing postoperative falls (Aim 2 in Figure 2)

Health-related quality of life

Random effects regression models based on PROC MIXED in SAS will be used to compare Physical Summary Score change over 12 months between the intervention and usual care group by introducing terms for time, indicator variables for treatment group and time x treatment group interactions with the latter set of regression coefficients of primary interest. The model will be controlled for baseline health-related quality of life. Potential confounding factors including age, gender and relevant comorbidities will be evaluated and controlled for in the model. We will utilize the same analysis approach to evaluate the Mental Summary Scores.

The analysis is primarily based on the following model: $Y_{it} = \alpha + \beta_1 t + \beta_{2A} X_{i1} + \beta_{3A} X_{i1}t + \beta_4 Y_{i0} + e_{it}$ (1) where Y_{it} = QOL for subject i at time t , where $t = 0$ for baseline, $t = 1$ for 12 months. $X_{i1} = 1$ if i th subject is in the Intervention group, = 0 otherwise $e_{it} \sim N(0, \sigma^2)$ β_{3A} is the mean difference in Physical Summary Score change between the Intervention and usual care groups. The coefficient β_{2A} allows for mean differences in Physical Summary Scores between groups at baseline. The coefficient β_4 allows the change in Physical Summary Score to depend on initial level.

Postoperative falls

Chi square test will be used to compare the incidence of falls at 12-months postoperatively between patients in the EEG-guided and in the usual care groups.

iii) Explore whether a multi-component safety intervention is associated with improved patient reported health-related quality of life and decreased incidence of postoperative falls (Aim 3 in Figure 2)

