Our sample size calculations are based on the anticipated delirium incidence and effect size for our primary endpoint analysis. Based on results of a previously published meta-analysis of four studies investigating the use of BIS-guided anesthetic administration, we conservatively assume an incidence of postoperative delirium in the routine anesthesia care group of 25%.²⁹ We performed a sample size sensitivity analysis and calculated different scenarios with different values for the delirium incidence in the intervention arm and corresponding power (80%, 90%, and 95%). With a two sided alpha $<5\%$ and 1,232 patients (616 per arm), the trial will have $>95\%$ power to detect an absolute decrease in delirium incidence $\geq 9\%$, $>90\%$ power to detect a decrease in delirium incidence $\geq 8\%$, and $>80\%$ power to detect a decrease in delirium incidence $\geq 7\%$. With a 7% decrease in delirium incidence, the 95% confidence interval would be approximately 3% to 12%. Even a 3% decrease in delirium incidence would be clinically important, suggesting that delirium would be prevented in one out of every 33 at risk patients who received EEG-guidance of general anesthesia.

ii) Health Related Quality of Life

The overall sample size of our study is defined through estimations of the primary outcome (delirium). For secondary analyses, we assume that ~80% of our trial population (~1,000 participants) will have completed the trial and the 1-year follow-up survey. With this sample size of 1,000, we can detect a difference of 0.5 points (standard deviation of 2.5) in the mean change of Physical Health Score from baseline to 1 year between the intervention and usual care group with a power of $>80\%$ and a two-sided alpha level of $p<0.05$.

iii) Postoperative Falls

This calculation is similarly based on the assumption that ~80% of our trial population (~1,000 participants) will have completed the trial and the 1-year follow-up survey. Based on a study that showed a preoperative fall prevalence of 33% over six months preoperatively in a similar patient population to the ENGAGES trial, we will conservatively assume an incidence of postoperative falls at 1-year in the routine anesthesia care group of 40%.¹¹⁰ With a sample size of 1,000, we will have $>80\%$ power to detect an absolute risk reduction of 12% between the EEG-guided and the usual care group at a two-sided alpha level of $p<0.05$.

Analysis of Pragmatic Elements of the ENGAGES Study

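### The primary delirium comparison is valid and meets its stated power, but it leaves unused the baseline delirium risk factors that the protocol names and plans to collect

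*Combined protocol and SAP*

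**What the plan says.** **Primary analysis.** Protocol, Statistical Analyses i) (Aim 1): "The incidence of delirium will be compared between groups using a chi-square test". The difference in incidence is reported with a 95% confidence interval. The same paragraph calls age, sex, history of falls and type of surgery known baseline delirium risk factors, but uses them only for exploratory tests of effect modification.

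**Risk factors named.** Protocol, Background: "consistently described risk factors for delirium include older age, male sex, mild cognitive impairment, dementia, sensory impairment, and chronic medical illness". The Delirium Prediction Models sub-study (Addendums, item j) adds ASA physical status, comorbidity and baseline cognition to the variables to be acquired. It uses them to predict delirium, not to estimate the arm effect.

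**Baseline collection.** Protocol, Cognitive Testing: as part of routine preoperative assessment, "patients will be screened for cognitive impairment with the AD-8 dementia screen" and with the Short Blessed Test. The Data Collection section and the prediction sub-study plan demographics, medical history and comorbidity at baseline.

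**Adjustment elsewhere.** The protocol's quality-of-life model controls for age, gender and comorbidities. The SAP, which covers one-year outcomes and not delirium, says for mortality: "Will perform unadjusted and adjusted analyses". It plans the same pair of analyses for quality of life and for falls. All three covariate lists include age, sex, ASA class, number of comorbid conditions and the Short Blessed Test.

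**The concern.** An unadjusted risk difference carries all of the between-patient variation in delirium risk, including the part that baseline data would explain. It also leaves any chance imbalance in age or cognition in the point estimate, since neither is a stratification factor. A risk difference standardised over a covariate model targets the same marginal quantity, usually with a smaller standard error.

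Three statements in the protocol make precision worth having here. It treats a p value just below 0.05 as preliminary and cites p<0.005 as the more stringent standard. It regards even a 3-point decrease as clinically important. And it says the decision on routine use will depend on the estimated effect size as well as on significance. The three main one-year hypotheses in the SAP have adjusted models; the outcome that sized the trial has none.

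**Working it through.** **Inputs from the documents.** Sample Size Calculations i): 616 per arm, two-sided 5%, and "we conservatively assume an incidence of postoperative delirium in the routine anesthesia care group of 25" percent. Stated power: above 80%, 90% and 95% for decreases of 7, 8 and 9 points.

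**Input not in the documents.** The share of outcome variance, R², that baseline data explain. I take 3% to 15% as an assumption. In a logit-normal risk model with mean risk 25%, this corresponds to an AUC of about 0.61 to 0.74.

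**Step 1: reproduce the plan's power.** With p₁ = 0.25, p₂ = 0.25 − d and p̄ their mean:

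power = Φ{ [d√n − 1.96·√(2p̄(1−p̄))] / √(p₁(1−p₁) + p₂(1−p₂)) }

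For d = 0.07: p̄ = 0.215, so √(2 × 0.215 × 0.785) = 0.5810. The denominator is √(0.1875 + 0.1476) = 0.5789. The numerator is 0.07 × 24.819 − 1.96 × 0.5810 = 0.5986. Power = Φ(1.034) = 84.9%.

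The same formula gives 93.2% for 8 points and 97.5% for 9. All three stated bounds hold without adjustment.

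**Step 2: unadjusted precision.** Half-width = 1.96 × √(0.3351/616) = 4.57 points.

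**Step 3: effect of adjustment.** Multiply the variance by (1 − R²), which is the same as replacing n by 616/(1 − R²). For 25% versus 18%:

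| R² (assumed) | AUC | Power | Effective total N = 1,232/(1 − R²) | 95% CI half-width = 4.57 × √(1 − R²) |
|---|---|---|---|---|
| 0 | 0.50 | 84.9% | 1,232 | 4.57 |
| 0.029 | 0.61 | 86.0% | 1,269 | 4.50 |
| 0.061 | 0.66 | 87.1% | 1,312 | 4.43 |
| 0.102 | 0.70 | 88.5% | 1,372 | 4.33 |
| 0.147 | 0.74 | 90.0% | 1,444 | 4.22 |

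**Step 4: other settings, same formula and R² range.**
- 5-point decrease at the 5% level: 55.6% unadjusted, 56.9% to 62.4% adjusted.
- 7-point decrease at p<0.005 (1.96 replaced by 2.807): 57.3% unadjusted, 59.0% to 66.7% adjusted.

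**Step 5: check the shortcut by simulation.** In 6,000 trials per setting, logistic regression on arm plus one risk score gave power of 85.7%, 87.6%, 87.8% and 90.4% for the four adjusted rows. These agree with the table to within about 1 point. With no true effect, the adjusted test rejected in 4.5% to 5.0% of trials across these rows. A second simulation fitted five covariates at R² of 0.044, 0.091 and 0.147. The standardised risk difference stayed centred on 7 points, and its variance was about 3%, 10% and 13% lower than that of the raw difference. The target is therefore kept, and a fitted model recovers roughly the calculated gain, sometimes slightly less.

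**The case against.** The strongest reply is that nothing in the plan is wrong. The chi-square matches the stated risk-difference target, its error rate and interval already allow for chance imbalance, and a simple comparison suits a pragmatic trial. This stands. A reader might infer that the trial is underpowered or the primary test invalid; Step 1 shows that neither follows.

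A reader might also infer that delirium is the only outcome left unadjusted. It is not. The protocol compares 12-month falls by chi-square. The SAP leaves patient-reported quality-of-life change, Barthel Index and return to work unadjusted, and its three main hypotheses pair adjusted with unadjusted analyses. Nor does the SAP comparison carry over fully. Its quality-of-life and falls analyses exclude patients without outcome data, so adjustment there can also address selective non-response, whereas delirium is assessed daily in hospital.

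Two further readings go beyond the text:
- That the covariates exist for every patient. Collection is planned, but ward enrolment is allowed and the SAP foresees missing values in a list that includes the Short Blessed Test.
- That the predictors are strong. The protocol gives no measure of strength, and the eligibility criteria (age, competence to consent, no preoperative delirium) narrow the covariate range.

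Finally, the calculated gain is not net of the randomisation factors. Surgery type and falls history are themselves called delirium risk factors, and the chi-square ignores them too. The share due to age, sex, cognition, ASA status and comorbidity alone cannot be separated from the documents. None of this removes the gain, but it limits what can be claimed about its size.

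**Conclusion.** The point holds as one of efficiency. The planned analysis is valid and adequately powered by its own criterion, but it gives up precision that data already planned for collection could supply. Under the assumed R² of 3% to 15%, the gain is about 1 to 5 percentage points of power at a 7-point decrease, and 0.07 to 0.35 points of confidence-interval half-width. In sample-size terms this is about 37 to 212 additional patients (1,269 − 1,232 and 1,444 − 1,232).

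The direction is secure if the covariates predict delirium, as the protocol says they do. The size rests on the assumed R², applies to the whole model including the randomisation factors, and may be slightly smaller once the model is fitted with imputed covariates.

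**What to change.** Before unblinding, prespecify the primary estimate as the standardised (marginal) risk difference, with 95% confidence interval and p value. Derive it from a logistic model with arm, the two randomisation factors (cardiac surgery, history of falls), age as a continuous variable, sex, Short Blessed Test score, ASA status and comorbidity count. Standardising keeps the risk difference that the protocol already reports and avoids moving to a conditional odds ratio.

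Use a simple imputation rule for missing baseline values, so that no randomised patient is dropped for a missing covariate. Keep the chi-square test and raw difference as supportive.

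The cost is some plan wording and a little more analysis code; no new data are needed. The one real constraint is that the covariate list and its coding must be fixed in advance. If allocation has already been revealed to the analysts, the adjusted estimate should be reported as supportive and labelled as not prespecified.

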### ***Hypothesis 2: Is EEG Guidance Intervention Associated with Improved Quality of Life One Year After Surgery?***

*Patient Population:* Patients randomized to intervention or control (N = 1232)

*Primary Predictor Variable:* EEG guidance intervention

(X=0 for control or X=1 for intervention)

Intention to treat

*Outcomes:* Veterans RAND 12-Item Health Survey (VR-12) physical component score (PCS), VR-12 mental component score (MCS), one year postoperatively

- Partially completed VR-12 surveys will not be scored and will be considered missing.

*Data Description Plan:* Box plots of VR-12 PCS and MCS at baseline, 30 days, and 1 year for the two groups. Provide median, interquartile range, and range at each time point.

*Analysis Plan:* Generalized linear model

$$y_{365} = \beta_0 + f(y_0) + \beta_1 x + \beta Z + \varepsilon$$

- In this equation,  $y_{365}$  is the quality of life (either VR-12 PCS or VR-12 MCS) at one year, and  $y_0$  is the quality of life metric at baseline.  $x$  is the EEG guidance intervention ( $x=0$  for control or  $x=1$  for intervention).  $Z$  is a vector of additional variables for which we will adjust.
- $f(y_0)$  is a potentially nonlinear function describing the relationship between baseline quality of life and quality of life at one year. This function will be modeled using splines.
- Will perform unadjusted ( $Z = \text{null}$ ) and adjusted ( $Z$  not null) analyses. Will adjust for age, sex, American Society of Anesthesiologists (ASA) physical status classification (1-2 vs 3 vs 4-5), number of comorbid conditions, baseline poor functional capacity (<4 METS), history of falls (yes/no within previous 6 months), evidence of abnormal cognition (preoperative Short Blessed Test score > 4), surgery type (cardiac versus non-cardiac), length of anesthesia (Anesthesia Stop – Anesthesia Start)
  - o Multiple imputation may be performed to address missing values of these variables
- Any patient with missing quality of life either at baseline or at one year will be excluded.
- $H_0: \beta_1 = 0$  (The null hypothesis is that the EEG guidance intervention has no association with postoperative quality of life.)

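### The protocol's quality-of-life model uses the baseline score as both outcome and covariate, so baseline adjustment has no effect on the treatment estimate and the standard error is too small

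*Combined protocol and SAP*

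**What the plan says.** Protocol, Statistical Analyses ii), Health-related quality of life: the physical and mental summary scores are to be compared using "Random effects regression models based on PROC MIXED in SAS". The analysis is built mainly on Model (1):

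Y_it = α + β1·t + β2A·X_i + β3A·X_i·t + β4·Y_i0 + e_it, with e_it ~ N(0, σ²)

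The time index is defined "where $t = 0$ for baseline, $t = 1$ for 12 months", so the baseline score is an outcome row. It is also the covariate Y_i0: "The model will be controlled for baseline health-related quality of life". The coefficient of interest, β3A, "is the mean difference in Physical Summary Score change between the Intervention and usual care groups". β2A is said to allow for arm differences at baseline, and β4 "allows the change in Physical Summary Score to depend on initial level". The equation contains no random effect, and no RANDOM or REPEATED structure is given.

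Protocol, Sample Size Calculations ii): with about 1,000 completers, "we can detect a difference of 0.5 points (standard deviation of 2.5) in the mean change of Physical Health Score", at more than 80% power and two-sided 5%.

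SAP, Hypothesis 2, Analysis Plan: the one-year score is modelled on arm, optional covariates and f(y0), where f "is a potentially nonlinear function describing the relationship between baseline quality of life and quality of life at one year". Here baseline is a covariate only. The SAP uses R and the protocol uses SAS 9.4. Neither document says that one model replaces the other.

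**The concern.** A baseline measurement can be an outcome row in a longitudinal model, or a covariate for later measurements. If it is both, the baseline rows ask the model to predict a value from itself. Three consequences follow.

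- The baseline adjustment does not reach the treatment effect, and the descriptions of β4 and β2A are wrong.
- The baseline rows fit too well. They pull down the pooled residual variance that sets the standard error of β3A, so the nominal 5% test rejects too often.
- The precision that adjustment for baseline should bring is lost.

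Health-related quality of life is listed as a key secondary outcome. The protocol's test of it is therefore invalid as printed, while a different and valid analysis of the same one-year scores stands in the SAP.

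**Working it through.** **Inputs.** From the documents: 1:1 allocation; about 1,000 analysed, so n = 500 per arm; 0.5 points difference in mean change; SD 2.5; two-sided 5%. Assumed: baseline to one-year correlation ρ from 0.3 to 0.7, equal variance σ² at both times, and complete data unless stated.

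**The plan's own power figure.** SE of the difference in mean change = 2.5·√(2/500) = 0.158. Then 0.5/0.158 = 3.16, and power = Φ(3.16 − 1.96) = 88.5%. This agrees with the stated >80%. The power statement is sound for a change-score comparison.

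**What β4 does.** Subtract the two rows of Model (1) for one patient:

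E[Y_i1 − Y_i0] = β1 + β3A·X_i

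β4 has gone. For the change to depend on initial level, the model needs a Y_i0 × t term. The least-squares estimate of β3A is the raw difference in mean change; in simulation the two agreed to about 3 × 10⁻¹⁶.

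**Where the fitted slope goes.** Within arm, the slope on Y_i0 is 1 in the baseline rows and ρ in the one-year rows. The pooled slope is (1+ρ)/2 (simulated 0.650, 0.750 and 0.850 at ρ = 0.3, 0.5 and 0.7). The fitted β2A is then 1 − (1+ρ)/2 = (1−ρ)/2 of the observed baseline difference, not the difference itself.

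**Residual variance.**

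- Baseline rows: σ²(1−ρ)²/4
- One-year rows: σ²(1−ρ)(5+3ρ)/4
- Mean of the two: σ²(1−ρ)(3+ρ)/4

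**Variance of the β3A estimate.**

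- Reported by the model: 4/n times the mean residual variance = σ²(1−ρ)(3+ρ)/n
- True: (2/n)·2σ²(1−ρ) = 4σ²(1−ρ)/n
- Ratio, model to true: (3+ρ)/4

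Type I error at nominal 5% is 2·[1 − Φ(1.96·√((3+ρ)/4))]. ANCOVA variance is 2σ²(1−ρ²)/n, so the change-score variance is 2/(1+ρ) times as large.

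| ρ | Model SE / true SE | Type I error, nominal 5% | Change-score / ANCOVA variance |
|---|---|---|---|
| 0.3 | 0.908 | 7.5% | 1.54 |
| 0.4 | 0.922 | 7.1% | 1.43 |
| 0.5 | 0.935 | 6.7% | 1.33 |
| 0.6 | 0.949 | 6.3% | 1.25 |
| 0.7 | 0.962 | 5.9% | 1.18 |

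Simulation (4,000 trials per ρ, 500 per arm) gave 6.8%, 6.4% and 6.2% for Model (1) at ρ = 0.3, 0.5 and 0.7, and 4.7% to 4.9% for ANCOVA.

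**Does a random intercept repair it?** The covariance between a patient's two residuals is −σ²(1−ρ)²/4, which is negative. A random-intercept variance that cannot go below zero is therefore estimated at zero, and the SE does not change. At ρ = 0.5 and σ = 1 it is 0.0591, against a true 0.0632.

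**Missing one-year scores.** With 616 per arm, 20% of one-year scores missing at random and every baseline row kept, simulated type I error was 10.1%, 9.8% and 9.0% at ρ = 0.3, 0.5 and 0.7.

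**Power lost on the plan's inputs.** With SD of change 2.5, the ANCOVA SE is 0.158·√((1+ρ)/2). Power is 97.5%, 95.5% and 92.9% at ρ = 0.3, 0.5 and 0.7, against 88.5%. For 80% power, ANCOVA needs 256, 295 and 334 per arm, against 393.

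**The case against.** **The SAP already settles it.** The SAP is a dedicated plan for one-year outcomes and its model is sound. It also appears to be the later text: it gives a closed surgery window ending in May 2018, while the protocol lists recruitment as open. This limits the practical harm. It does not close the point, because neither document says that the SAP model replaces Model (1).

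**The standard error depends on a covariance that is not stated.** This is correct. A compound-symmetric structure that allows negative covariance gives the right SE (0.0632 at ρ = 0.5). But the protocol states no such structure. It prints independent errors and names random effects, and both leave the SE too small. Even with the covariance repaired, the β4 statement stays false and the loss against ANCOVA remains.

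**A change-score contrast is valid and is what was powered.** Also correct. With complete data, randomisation keeps β3A unbiased, and 88.5% power meets the stated target. The lower efficiency alone would not be an error. It matters here because the protocol says that the model controls for baseline.

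**The inflation is modest.** With complete data it is one to two and a half percentage points. It is larger if patients with only a baseline score stay in the model.

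**Conclusion.** The concern holds for Model (1) as printed. That β4 cancels from the change and that β3A is the raw change-score difference are algebra and need no assumption about ρ. The SE claim rests on the printed independent errors, or on a random intercept bounded at zero. For ρ from 0.7 down to 0.3, two-sided type I error is 5.9% to 7.5% with complete data and equal variances. With unequal variances the SE is still never too large, and it is correct only if the slope of the one-year score on baseline is exactly 1. The variance is 18% to 54% above that of ANCOVA. At a nominal 0.005 the error would be about 0.7% to 1.1%, although the formal 0.005 tier is in the SAP; the protocol mentions that threshold only when discussing the delirium result. The fault lies in the standard error and the precision, not in bias. It affects a key secondary outcome and should be corrected.

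**What to change.** In the protocol, delete Model (1) and its statements about β2A and β4. State that the physical and mental component scores are analysed with the SAP's Hypothesis 2 model: the one-year score on arm and a function of baseline, with baseline never an outcome row. Say explicitly that this model governs.

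If a longitudinal model is wanted, use only the 30-day and 12-month scores as outcomes, with baseline as covariate and an unstructured within-patient covariance. A smaller repair would keep both rows, drop the Y_i0 covariate and state the covariance. That gives a valid change-score test but gives up the gain in precision.

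The cost is wording only. No new data are needed, the replacement model is already in the SAP, and the power statement can stay: for the same 0.5 points and SD of change 2.5, ANCOVA has at least 92.9% power over the range of ρ shown.
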